- To evaluate the utility of an investigator static global tumor assessment (ISGTA) in assessing the proportion of baseline treatment-targeted BCCs that are evaluated as being clear or almost clear.
- Histologic Cure: The proportion of the excisional samples obtained at or shortly after the Week 12 visit that demonstrate no residual BCC.

Statistical Methods:

All subjects who are randomized and dispensed study drug will be included in the intent-to-treat (ITT) analysis set. All subjects who are randomized, receive at least one confirmed dose of study drug, and have at least one post-baseline safety assessment will be included in the safety population.

No imputation will be made for the primary endpoint. For the secondary endpoint, last observation carried forward (LOCF) will be used to impute efficacy data that are missing post-baseline through Week 12. No imputations will be made for missing safety data.

Per protocol analysis will be performed – we will exclude samples with insufficient BCC, subjects with poor treatment compliance, or tumors where the diameter was incorrectly measured based on review of photographs. We will also analyze BCC size change based on photographs.

Efficacy Summaries:

The efficacy endpoints are intended to compare once and twice daily application of 2% patidegib gel, 4% patidegib gel, and vehicle gel. Efficacy assessments will be summarized descriptively by treatment group and visit.

Primary Efficacy Endpoints:

• Change in GLI1 mRNA levels in drug-treated vs. vehicle-treated tumors after 12 weeks of treatment.

Secondary Efficacy Endpoint:

• Decrease in tumor size defined as percent decrease in the greatest diameter of baseline treatment-targeted BCCs at the Week 12.

Exploratory Efficacy Endpoint:

- The proportion of baseline treated tumors are smaller based on photographic review
- The proportion of baseline treatment targeted BCCs that are evaluated as being clear or almost clear at Baseline, Weeks 2, 6, 8, 10, and 12 based on the ISGTA.

Efficacy Analyses:

The primary endpoint and the secondary endpoints of change in tumor size, and reduction in the HH signaling pathway will be evaluated with an analysis of covariance (ANCOVA) with treatment group as factor and baseline value as a covariate. Pairwise comparisons will be performed using contrasts within the ANCOVA. Additionally, t-tests for pairwise comparisons of the primary endpoint will be done, or alternatively a non-parametric approach may be used.

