10.1 Analysis Populations

Per protocol analysis will be performed —samples with insufficient BCC, subjects with poor treatment compliance, or tumors where the diameter was incorrectly measured based on review of photographs will be excluded. BCC size change based on photographs will also be analyzed. Safety analyses will be performed using the safety population. All subjects who are randomized, receive at least 1 confirmed dose of study drug and have at least one post-baseline safety assessment will be included in the safety analysis set.

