6.4.3 Per Protocol (PP) Population

All subjects in the ITT population who complete the Week 12 evaluation without any significant protocol violations will be included in the PP population and analyzed according to the treatment group they received. The PP population will include subjects in the safety population who do not meet any of the following criteria:

- Violated the inclusion/exclusion criteria;
- Have taken any interfering concomitant medication;
- Did not attend the Week 12 visit;
- Have not been compliant with the dosing regimen, between 80% to 120%
- Had samples with insufficient BCC
- Had tumors where the diameter was incorrectly measured based on review of photographs

Subjects that discontinue from the study due to an adverse event related to study treatment or documented lack of treatment effect will be included in the PP population. Prior to breaking the blind, other additional criteria may be added to the list to accommodate for unforeseen events that occurred during the conduct of the trial that result in noteworthy study protocol violations.

Efficacy analyses performed on a by-tumor basis will include tumors from subjects who are not excluded for any of the above reasons.

All efficacy analyses will be performed on the ITT population as well as on the PP population.

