6.7 Analysis of Efficacy

All efficacy analysis will be done on both the ITT and PP populations.

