8. CHANGES IN THE PLANNED ANALYSES

The protocol defines the secondary objective as the clinical efficacy of patidegib as defined by the percent decrease in greatest diameter of baseline treatment targeted basal cell carcinomas after 12 weeks of treatment. The secondary objective will now also include the clinical efficacy of patidegib as defined by the proportion of Complete or Partial Response in treatment targeted BCCs after 12 weeks of treatment as defined by blinded photographic review. References

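### Read literally, SAP 6.4.3 turns the protocol's sample- and tumor-level Per Protocol exclusions into whole-subject exclusions, and SAP section 8 does not declare the change

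*SAP*

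**What the plan says.** Protocol 10.1 describes the PP analysis in terms of three different units: "samples with insufficient BCC, subjects with poor treatment compliance, or tumors where the diameter was incorrectly measured based on review of photographs will be excluded". The synopsis, under Statistical Methods, does the same: "we will exclude samples with insufficient BCC, subjects with poor treatment compliance, or tumors where the diameter was incorrectly measured". Only the compliance exclusion is attached to subjects.

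SAP 6.4.3 starts from a subject-level stem: "The PP population will include subjects in the safety population who do not meet any of the following criteria". The list beneath it contains "Had samples with insufficient BCC" and "Had tumors where the diameter was incorrectly measured based on review of photographs". The section then adds, for tumor-based analyses: "Efficacy analyses performed on a by-tumor basis will include tumors from subjects who are not excluded for any of the above reasons".

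SAP 6.7 applies this population widely: "All efficacy analysis will be done on both the ITT and PP populations". SAP section 8, where departures from the protocol's analyses are declared, reports one change, the added photographic response objective: "The secondary objective will now also include the clinical efficacy of patidegib". It does not mention the PP definition.

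**The concern.** A subject may have one or two treated tumors, and the GLI1 analysis in SAP 6.7.1 is by tumor. If the SAP is programmed as worded, a single inadequate sample or badly measured tumor takes out everything that subject contributes to PP: the other tumor, and the diameter, photographic response, ISGTA and area data whose validity does not turn on that item. Each active regimen has 6 planned subjects, so one exclusion is 1/6 = 17% of the arm (1/12 = 8% of the pooled vehicle group).

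The insufficient-BCC criterion also names neither a visit nor a cause. It can cover a thin screening biopsy. It can equally cover a Week 12 excision in which no tumor is left, which the synopsis treats as histologic cure under its exploratory measurements. A subject could therefore leave every PP table because a tumor cleared. The PP tables are a companion to ITT for every efficacy endpoint in a trial meant to inform dose and regimen, so their membership rule should be the intended one and should be unambiguous.

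**Working it through.** **1. Units side by side.**

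| Exclusion | Protocol synopsis and 10.1 | SAP 6.4.3, literal |
|---|---|---|
| Insufficient BCC | sample | subject |
| Poor compliance | subject | subject |
| Mis-measured diameter | tumor | subject |

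**2. Does anything restore the protocol's units?** The by-tumor sentence in 6.4.3 admits a tumor only if its subject has not been excluded, so it repeats the subject rule. SAP 6.1.9 only points to the definition. SAP 6.2 and Listing 16.2.3 record exclusions by subject. SAP 6.7.1 to 6.7.3 set no further tumor or sample rule, and section 8 is silent.

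**3. What the SAP adds.** The protocol's own rule already removes an insufficient sample from PP, also without naming a visit or cause. A Week 12 sample with no BCC is thus lost to PP GLI1 under either document. The SAP adds the loss of the subject's other tumor and of the other endpoints.

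**4. Scale, for illustration.** There is no plan figure to reproduce. From the documents: 6 active subjects per cohort (SAP 4.1) and at most two tumors each (synopsis, Methodology). Assumed: a chance q = 5%, 10% or 20% that a tumor triggers an exclusion, and the number n2 of the 6 subjects with two tumors.

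- Tumor-level rule: expected tumors lost = (6 + n2)q.
- Subject-level rule: expected tumors lost = (6 − n2)q + 2·n2·(1 − P00), where P00 is the chance that neither tumor triggers. P00 = (1 − q)² if the two are independent.

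All with two tumors, q = 10%: subject rule 12 × (1 − 0.81) = 2.28; tumor rule 12 × 0.10 = 1.20.

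| Arm of 6 | Subject rule, q = 5/10/20% | Tumor rule |
|---|---|---|
| All two tumors (12), independent | 1.17 / 2.28 / 4.32 | 0.60 / 1.20 / 2.40 |
| All two tumors, latent correlation 0.5 | 1.05 / 2.01 / 3.75 | 0.60 / 1.20 / 2.40 |
| Half two tumors (9), independent | 0.74 / 1.44 / 2.76 | 0.45 / 0.90 / 1.80 |
| One tumor each (6) | 0.30 / 0.60 / 1.20 | 0.30 / 0.60 / 1.20 |

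The chance that at least one of the 6 subjects is excluded is 1 − (1 − q)^12 = 46/72/93% with two tumors each (independent), and 1 − (1 − q)^6 = 26/47/74% with one.

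**5. Carry-over between endpoints.** Assume per tumor 20% insufficient BCC and 10% mis-measured diameter, independent. If the diameter exclusion does not touch GLI1, 80% of tumors stay for PP GLI1. Under the literal SAP, 0.80 × 0.90 = 72% stay in one-tumor subjects and 0.72² = 52% in two-tumor subjects. The protocol does not say whether its exclusions are endpoint-specific. If its tumor exclusion does apply to GLI1, the contrast is 72% against 72% with one tumor and 72% against 52% with two.

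**The case against.** The strongest reply is that the SAP authors meant no change. Both bullets keep the protocol's nouns, and the by-tumor sentence is redundant if whole subjects are already gone, so a tumor-level intent is plausible. That stands as a reading of intent, and a reader should not infer a deliberate change of rule. It does not rescue the wording: the stem and the by-tumor sentence both attach exclusion to subjects, and two programmers could build different PP sets.

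The consequence is also limited. Every efficacy analysis is repeated on ITT, p-values are descriptive (SAP 5.1), and GLI1 is not imputed, so a sample that yields no value is missing in both populations. Exclusion reasons are listed by subject and residual-tumor status is listed, so causes could largely be reconstructed, although no planned table shown counts them by arm. All of this stands and lowers the weight of the point.

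A reader might infer that the SAP rule strips responders from PP and biases it in a known direction. The documents do not support that. Part of the dependence on outcome is in the protocol's own sample rule. Protocol 5.1 expects enough residual tumor at Week 12 for biomarker work, and absence of BCC on histology is not the photographic Complete Response of SAP 5.1.2.

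A reader might also count four samples per two-tumor subject and multiply one failure rate across them. That assumes equal rates at both visits. Nothing supports this, since the pre-treatment biopsy must already have confirmed nodular BCC for entry.

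**Conclusion.** The PP rule is wrong as written: taken literally, SAP 6.4.3 widens two of the protocol's three exclusions to the whole subject, and section 8 does not say so. The effect is confined to the PP tables. Its size depends on two quantities that the documents do not give, the share of two-tumor subjects and the rate of insufficient or mis-measured items. Over the assumed range, the extra loss in a 6-subject arm runs from none (one tumor each) to 0.6, 1.1 or 1.9 of 12 tumors (two tumors each, independent, q = 5/10/20%), plus carry-over to endpoints that do not depend on the failed item. The direction and size of any bias are undetermined. Severity is minor to should-fix, and confidence is moderate because the by-tumor sentence may have been meant to keep the protocol's units.

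**What to change.** In SAP 6.4.3, remove the two bullets as subject-level criteria and state:

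> A sample with insufficient BCC is excluded from the PP GLI1 analysis for that tumor. A tumor whose diameter was incorrectly measured is excluded at the tumor level. The subject's other tumor stays in PP. A Week 12 sample with no residual BCC may leave that tumor without a GLI1 value, but the subject and tumor stay in PP for the diameter, photographic response, ISGTA and area analyses.

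Amend the by-tumor sentence to match. Declare in section 8 that the insufficient-BCC exclusion is limited to GLI1, and declare any similar limit on the diameter exclusion, because the protocol states neither. If the sponsor prefers the subject-level rule, declare and justify that in section 8 instead.

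Add a small table by arm of insufficient samples by visit. Listing 16.2.6.2 carries cell counts and QC status by visit and tumor site. Listing 16.2.6.3 adds Week 12 residual-tumor status, but shows nothing that would identify an inadequate baseline biopsy. Settle the wording before the first sponsor and CRO unblinding described in SAP 4.1.3 and 6.1.6, so that the rule is not chosen with results known.

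The cost is SAP wording and one table from data already planned for listing. The drawback is that PP denominators will differ between endpoints and must be shown.

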6.5 Demographic and Other Baseline Characteristics

All baseline summaries will be done on the ITT population.

Sex, race, and ethnicity will be summarized by counts and percentages. Age, height (cm), and weight (kg) will be summarized with descriptive statistics.

Medical histories will be coded using the MedDRA dictionary and presented in a by-subject listing.

6.6 Prior and Concomitant Medications

Concomitant therapies will be coded to preferred name and Anatomical Therapeutic Chemical (ATC) classification of ingredients using the World Health Organization (WHO) Drug dictionary (WHO-DDE).

A by-subject listing of all prior and concomitant medications will be presented. Medications that start prior to first dose but continue after the first dose will be considered a concomitant medication. Medications that are unable to be classified as either prior or concomitant due to missing data will not be considered a concomitant medication.

6.7 Analysis of Efficacy

All efficacy analysis will be done on both the ITT and PP populations.

6.7.1 Primary Efficacy Analysis

The primary endpoint of change in GLI1 mRNA levels will be evaluated with an analysis of covariance (ANCOVA) with treatment group as factor and baseline value as covariate. Analysis is on a by tumor level. Pairwise comparisons as well as any treated (combining all patidegib groups) versus vehicle will be performed using contrasts within the ANCOVA.

Additionally, if number of results is sufficient, a t-test will be done to perform pairwise comparisons of change in GLI1 mRNA levels of each treatment group with vehicle (and combined patidegib versus vehicle). If assumptions required for a t-test are not met, then a Mann Whitney U test will be performed.

Data will be summarized by visit. Both change from baseline and percent change from baseline will be presented.

This analysis will be done for 2 regions (1) BCC and (2) BCC + tumor-associated stroma.

No imputation on GLI1 data will be performed.

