Approximately 36 subjects who meet the study entry criteria will be enrolled into one of four sequential cohorts. As soon as one cohort has been completely enrolled, the next cohort will be enrolled. Each subject will treat no more than two previously untreated biopsy confirmed treatment-targeted nodular BCCs. If the subject has additional non-treatment targeted BCCs they can be treated surgically or with topical agents prior to or during the trial. Within each cohort subjects will be randomized in a 2:1 ratio to receive active or vehicle gel. The sequential cohorts will be:

- Cohort 1: patidegib gel 2% or vehicle, once daily
- Cohort 2: patidegib gel 4% or vehicle, once daily
- Cohort 3: patidegib gel 2% or vehicle, twice daily
- Cohort 4: patidegib gel 4% or vehicle, twice daily

The study drug will be applied topically to the treatment-targeted BCCs and a rim or adjacent skin for 12 weeks.

Information on reported and observed adverse events (AEs) will be obtained at each visit. An abbreviated physical examination (PE) will be performed at Baseline and Week 12.

The treatment-targeted BCCs will be identified by the Investigator at the Baseline visit and will be circled in ink at Baseline, Weeks 6 and 12, and photographed, and measured at all study visits (Baseline, Weeks 2, 6, 8, 10, and 12).

Blood samples for complete blood count and serum chemistry and urine for urinalysis will be collected from subjects at Screening, Week 6, and Week 12.

Subjects who terminate study participation early will be asked to complete all Week 12 assessments, as appropriate, prior to commencement of any alternative therapy for BCCs (if possible). Subjects who discontinue from the study during the treatment period will not be replaced.

If signs or symptoms develop in the treatment areas during the treatment period that restrict daily activities or make continued application of the study drug difficult due to discomfort, the Investigator may instruct the subject to interrupt use of the study drug temporarily and to resume application of the study drug once the signs and symptoms have resolved adequately to the point that the Investigator believes that treatment can safely be resumed. The

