¹ For the purpose of this trial, a female not of childbearing potential is defined as a sexually mature woman who: 1) has undergone a hysterectomy or bilateral oophorectomy; or 2) has been naturally postmenopausal for at least 12 consecutive months (i.e., has not had menses at any time in the preceding 12 consecutive months); or 3) is 41 years of age or older with physiologic symptoms of menopause and a Follicle Stimulating Hormone (FSH) level of ≥ 30 IU/L or 4) whose male sexual partner has had a vasectomy.

occurring inhibitor of SMO, and the unknown level of systemic exposure following topical application of patidegib in humans.

- 4. If the subject is a male with a female sexual partner who is of childbearing potential, the couple is willing to use two effective methods of birth control during the duration of the trial and for one month after the last application of the gel. Authorized birth control methods are outlined in Inclusion Criterion #3. Any woman of childbearing potential applying the gel to themselves, or assisting a subject, must comply with the same birth control measures.
- 5. One or two previously untreated BCCs with the clinical features of a nodular BCC confirmed by a biopsy done at or prior to screening confirming nodular BCC. These tumors must be suitable for surgical excision. The BCCs prior to biopsy must be no less than 5 mm or greater than 15 mm in greatest diameter on the face and no less than 9 mm or more than 20 mm in greatest diameter at sites other than the face. Tumors on the nose, periorbital skin, or on or below the knee are excluded.
- 6. The subject is willing to abstain from application of non-study topical prescription and over the counter medications within 5 cm of a treatment-targeted BCC for the duration of the study except as prescribed by the Investigator. Moisturizers and emollients are allowable. Subjects will be encouraged to use sunscreen with a sunscreen protection factor (SPF 15 or higher) at least once daily on all exposed skin sites.
- 7. Female subjects must have negative serum pregnancy test at Screening.
- 8. The subject is willing to contact the study center after each primary skin care physician (PSCP) visit to provide the study center details of the visit and any treatment of skin tumors.
- 9. The subject is willing to forego alternative treatment of the treatment-targeted baseline BCC for the duration of the trial.

Exclusion Criteria:

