4. STUDY DESIGN

4.1 Overall Study Design

This is a double-blind, dose escalating, randomized, vehicle-controlled study designed to assess the efficacy and safety of patidegib gel 2% and 4% in comparison with vehicle applied once or twice daily. The population of subjects will be enrolled from the **PPD**

Approximately 36 subjects who meet the study entry criteria will be randomized to one of four sequential cohorts. Each cohort will have 6 subjects randomized to active drug and 3 randomized to vehicle. The four sequential cohorts will be:

- Cohort 1: patidegib gel 2% or vehicle applied once daily,
- Cohort 2: patidegib gel 4% or vehicle applied once daily,
- Cohort 3: patidegib gel 2% or vehicle applied twice daily, and
- Cohort 4: patidegib gel 4% or vehicle applied twice daily.

As soon as one cohort has been enrolled the next cohort will be recruited. The study drug will be applied topically to the treatment-targeted nodular BCCs once or twice daily for 12 weeks of treatment.

Upon completion of the 12-week treatment period, all subjects will be asked to return to the investigational center for final evaluation. At the Week 12 visit the treatment site(s) will be excised. The area excised should at a minimum include the original diameter of the tumor. This means that if the tumor has shrunk in size the entire original area of the BCC will be excised, not just the visually apparent residual tumor. During the study, subjects will be allowed to use moisturizers and emollients and sunscreen. The Investigator will assess the areas affected at each visit.

The treatment-targeted BCC(s) will be identified by the Investigator at the Baseline visit and will be circled in ink at Baseline, Weeks 6 and 12, and photographed, and measured at all study visits (Baseline, Weeks 2, 6, 8, 10, and 12).

Biomarkers: On each subject one or two baseline previously untreated nodular BCCs designated as a treatment-targeted tumor will be biopsied and at the end of 12 weeks of treatment the treatment site(s) will be excised. Both samples will be evaluated histologically and for determination of GLI1 mRNA levels.

Blood samples for complete blood count and serum chemistry and urine for urinalysis will be collected from subjects at Screening, Week 6, and Week 12.

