6. STATISTICAL AND ANALYTICAL PLANS

6.1 General Methodology

All statistical processing will be performed using Statistical Analysis System (SAS®) unless otherwise stated. No interim analyses are planned. If determined appropriate by the Sponsor, limited safety and efficacy interim analysis on tumor shrinkage and biomarkers may be performed.

Formal inferential testing will not be performed, however p-values will be provided for descriptive purposes. Descriptive statistics will be used to provide an overview of the efficacy and safety results. P-values which are supplied are for descriptive purposes only. For categorical parameters, the number and percentage of subjects in each category will be presented. For continuous parameters, descriptive statistics will include n (number of subjects), mean, standard deviation (SD), median, minimum (min), and maximum (max). For by treatment group summaries the vehicle gel group from each cohort will be combined into a single group.

The last observation carried forward method (LOCF) will be used to impute missing secondary and exploratory efficacy data (i.e., the last available on-therapy observation for a subject will be used to estimate subsequent missing data points). Analyses will also be carried out on an 'as

observed' basis without imputation. No imputations will be made for missing primary endpoint data or safety data.

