6.1.4 Adjustments for Covariates

Treatment group as factor and baseline values as covariate will be included in the primary and secondary endpoints analyses.

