6.7.2 Secondary Efficacy Analysis

The first secondary endpoint, the proportion of treatment targeted BCCs with Complete or Partial Response as determined by blinded photographic review will be evaluated using a 2-sided Fisher's Exact test. This analysis will be performed on all available data with no imputation of missing data. Both pairwise comparisons between treatment groups and all treated (combining all patidegib groups) versus vehicle will be done.

The second secondary endpoint, the greatest diameter of all treatment targeted BCCs, will be evaluated similarly to the primary endpoint. This analysis will be performed using LOCF imputation as well as 'as observed' (i.e. no imputation of missing data).

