6.7.3 Exploratory Efficacy Analysis

The exploratory endpoint of investigator static global tumor assessment (ISGTA) will be summarized by visit on a by tumor level. Proportion with success as defined by Clear/Almost Clear will be provided. Results will be analyzed with a Cochran-Mantel-Haenszel (CMH) test.

Tumor area will be evaluated with an analysis of covariance (ANCOVA) with treatment group as factor and baseline value as covariate. Analysis is on a by tumor level. Pairwise comparisons as well as any treated (combining all patidegib groups) versus vehicle will be performed using contrasts within the ANCOVA.

The proportion of baseline treated tumors are smaller at each study visit based on photographic review will be summarized by treatment group. Results will be analyzed between groups and all treated (combining all patidegib groups) versus vehicle with a CMH test. Tumor area will be summarized by visit.

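### GLI1, diameter and area p-values treat tumours as independent although subjects are randomised and may contribute two; they are too small on average if paired tumours are positively correlated

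*SAP*

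**What the plan says.** **Unit of randomisation.** Subjects are randomised within four sequential cohorts: "Each cohort will have 6 subjects randomized to active drug and 3 randomized to vehicle" (SAP 4.1). SAP 6.1 pools the vehicle subjects of all cohorts into one group.

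**Tumours per subject.** Inclusion criterion 5 admits subjects with "One or two previously untreated BCCs with the clinical features of a nodular BCC", and the synopsis sets the ceiling: "Each subject will treat no more than two previously untreated biopsy confirmed treatment-targeted nodular BCCs". Two-tumour subjects are clearly expected. Protocol 5.1 works out a total dose for someone treating two tumours, Protocol 6.3 has a rule for a subject with two target tumours, and SAP Listing 16.2.6.1 is laid out with two tumour rows per subject and visit.

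**Unit of analysis.** For GLI1, SAP 6.7.1 says "Analysis is on a by tumor level". On model terms, SAP 6.1.4 says only: "Treatment group as factor and baseline values as covariate will be included in the primary and secondary endpoints analyses". Greatest diameter "will be evaluated similarly to the primary endpoint" (SAP 6.7.2), and its table shell counts tumours. SAP 6.7.3 repeats the by-tumour ANCOVA for area and says that ISGTA "will be summarized by visit on a by tumor level". The shell footnotes confirm the two-term model. Neither document specifies a random subject effect, a clustered variance, averaging within subject or a rule to use one tumour per subject.

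**Status of the p-values.** "P-values which are supplied are for descriptive purposes only" (SAP 6.1).

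**The concern.** Both tumours of a subject are always in the same arm. If they tend to respond alike, the second carries less information about the treatment contrast than a tumour from another subject would. A model that treats them as independent understates the standard error, uses too many residual degrees of freedom, and returns p-values that are too small on average. The by-tumour t-test or Mann-Whitney test for GLI1 and diameter shares the fault. The by-tumour CMH tests (ISGTA, smaller/not smaller) are exposed to it as well.

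The shells print a p-value for every pairwise contrast and for all patidegib versus vehicle, with no standard errors or confidence intervals, so the p-value is the only measure of uncertainty on a treatment comparison. The trial is meant to inform the dose and regimen for later studies (Protocol 4, SAP 2), and the unblinded sponsor looks at efficacy after Cohorts 1 and 2 and again after Cohort 3 (SAP 6.1.6). These numbers will be read. SAP 6.1 defines n as subjects while the efficacy shells count tumours, so the tables would not show how many subjects stand behind each result.

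**Working it through.** **Inputs from the documents.** 4 × (6 + 3) = 36 subjects, which agrees with the planned number of approximately 36. Groups for analysis: 6 subjects on each of four regimens and 4 × 3 = 12 on vehicle. Each subject has one or two tumours. Model: treatment group (five levels) plus baseline, so six parameters. The plan states no power, alpha, SD or effect size, so there is no sponsor figure to reproduce.

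**Assumed inputs.** f is the share of subjects with two tumours and ρ the within-subject correlation. The documents give neither, so ranges are used.

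**Degrees of freedom.** If every subject has two tumours, the by-tumour model has 72 − 6 = 66 residual degrees of freedom. One value per subject gives 36 − 6 = 30.

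**Closed form.** With m tumours per subject, the variance of a group mean over tumours is inflated by DE = 1 + ρ(Σm²/Σm − 1). Per subject, Σm² averages 1 + 3f and Σm averages 1 + f. The actual error at nominal 5% is 2[1 − Φ(1.96/√DE)]. For f = 0.5 and ρ = 0.5: DE = 1 + 0.5 × (2.5/1.5 − 1) = 1.333, and the error is 2[1 − Φ(1.697)] = 9.0%.

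**Simulation of the planned ANCOVA, no treatment effect.** 10,000 runs per setting with groups of 12/6/6/6/6 subjects. Baseline and residual are both correlated ρ within subject, and the outcome is −0.5 × baseline plus residual. Entries are percent rejected at nominal 5%.

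| f | ρ | DE | Closed form | One regimen vs vehicle | All patidegib vs vehicle |
|---|---|---|---|---|---|
| 25% | 0.3 | 1.12 | 6.4 | 6.4 | 6.4 |
| 25% | 0.5 | 1.20 | 7.4 | 7.4 | 7.0 |
| 25% | 0.7 | 1.28 | 8.3 | 8.9 | 8.6 |
| 50% | 0.3 | 1.20 | 7.4 | 7.0 | 7.6 |
| 50% | 0.5 | 1.33 | 9.0 | 9.2 | 8.9 |
| 50% | 0.7 | 1.47 | 10.6 | 10.6 | 11.1 |
| 100% | 0.3 | 1.30 | 8.6 | 9.0 | 9.0 |
| 100% | 0.5 | 1.50 | 11.0 | 12.0 | 11.2 |
| 100% | 0.7 | 1.70 | 13.3 | 14.5 | 14.5 |

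Controls behave as they should: f = 0 gives 4.9% and 5.0%, and ρ = 0 gives 4.6–5.3%. The same ANCOVA on one mean per subject gives 4.6–5.5% in every setting.

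**All planned tests.** 8,000 trials per setting, Monte Carlo error about ±0.5 points, baseline–change correlation assumed −0.4. Contrasts: 4% BID vs vehicle, all active vs vehicle, and 2% QD vs 4% BID (first two only for t-test and Mann-Whitney). Binary endpoints assume response rates of 30% and 50%. Each range covers ρ from 0.3 to 0.7.

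| By-tumour test | f = 10% | 25% | 50% | 100% |
|---|---|---|---|---|
| ANCOVA | 5.1–7.0 | 6.3–8.6 | 7.3–11.2 | 8.6–15.0 |
| t-test | 5.2–6.6 | 6.1–8.4 | 7.2–10.9 | 8.2–14.4 |
| Mann-Whitney | 4.8–5.9 | 6.1–8.0 | 6.7–9.9 | 7.9–13.6 |
| CMH | 4.2–6.5 | 5.8–8.6 | 7.0–11.6 | 7.8–16.4 |
| Fisher | 1.2–4.7 | 2.8–5.8 | 3.8–8.6 | 3.8–11.3 |

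At ρ = 0.1 the ANCOVA stays at 5.0–6.4% for every f.

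**Replacements, same settings.** ANCOVA on subject means 4.6–5.7%; t-test on subject means 4.5–5.5%; Mann-Whitney on subject means 3.8–5.3%; random subject intercept by REML with subjects − 6 degrees of freedom 3.9–5.7% (3,000 trials); rank test on each subject's proportion of responding tumours 2.2–5.6%.

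**The case against.** The plan uses no significance level. SAP 6.1.8 says inferential tests will not be performed, and no decision rule depends on a p-value. This stands and limits the seriousness, but a p-value labelled descriptive should still describe the precision of the data correctly.

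Both f and ρ are unknown, and the largest figures need every subject to have two tumours with ρ = 0.7. Eligible tumours must be untreated, biopsy-confirmed nodular lesions within size and site limits, and basal cell nevus syndrome is excluded, so a low f is plausible. A low ρ is possible too: Protocol 4 says about 10% of sporadic BCCs carry an SMO mutation, which is a property of the tumour. This also stands. At f = 10% or ρ = 0.1 the low ends cannot be told apart from 5%.

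Too small is true on average, not for every result. In a null simulation at ρ = 0.5 (4% BID vs vehicle), the by-tumour ANCOVA p-value was below the subject-mean one in 56%, 60%, 65% and 92% of trials for f = 10%, 25%, 50% and 100%. A single p-value can move either way; that does not make the test correctly calibrated.

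Fisher's test for complete or partial response is conservative at these sizes and exceeds 5% only under stronger clustering, so the case for replacing it is weaker.

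The remedies have limits. The REML subject variance was estimated as zero in 20–27% of trials at f = 10% (ρ 0.3–0.5) and in 7–20% at f = 25%; the fit then returns the by-tumour estimate with only the degrees of freedom changed. Subject means weight subjects equally while the displayed means weight tumours equally. Both points should be stated in the SAP; neither argues for leaving the subject out.

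**Conclusion.** The plan is wrong as written on this point. It randomises subjects, allows two tumours in each, and tests GLI1 change, diameter and area as if every tumour were independent. Whenever paired tumours are positively correlated, the ANCOVA and t-test or Mann-Whitney p-values overstate the evidence on average, and so do the CMH p-values except where two-tumour subjects are few. For ρ between 0.3 and 0.7 the ANCOVA error ranges from barely above 5% when few subjects have two tumours to about 15% when all do. There is no inflation if no subject has two tumours or if pairs are uncorrelated.

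This should be fixed before the analysis, but the trial does not fail on it. The fault lies in the p-values alone.

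**What to change.** Amend SAP 6.1.4 and 6.7.1–6.7.3 as follows.

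- Keep all tumour-level descriptive summaries.
- Take the GLI1, diameter and area p-values from an ANCOVA on subject means, or from a tumour-level ANCOVA with a random subject intercept. For the latter, name the small-sample degrees of freedom (subjects − 6 was adequate above). Subject means are simpler and avoid the zero-variance problem. State that they weight subjects equally.
- Run the t-test or Mann-Whitney test on subject means.
- For complete/partial response, ISGTA and smaller/not smaller, keep the tumour-level proportions but take p-values from a rank test on each subject's proportion of responding tumours. Permutation within cohort is an option for active versus vehicle only; it cannot compare regimens, because each cohort holds one regimen plus vehicle.
- Show the number of contributing subjects beside the number of tumours in every efficacy table, since the header N is the population count. Reporting how many subjects per group have two tumours would also help.

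**Cost.** SAP wording and a little programming, with no protocol change; the endpoints stay defined on tumours. P-values become slightly less favourable on average. For an assumed effect of 1 SD, power differs by at most about 2 points between the two ANCOVA options. The rank test is conservative for six-versus-six regimen comparisons (error down to about 2–3% in some settings). If no subject turns out to have two tumours, the subject-mean ANCOVA is identical to the planned one.
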